Additionally the PRAC requested that the MAHs should submit a risk management plan (RMP) within 3 months after the EC decision. The protocols of two studies - a drug utilization study (DUS) and a PASS should be submitted as part of the RMP.

Hormosan Pharma GmbH launched Flupirtinmaleat-Hormosan 100 mg Hartkapseln in Germany on 31 July 2012, but the marketing of the product was stopped in January 2013. This decision was taken because of commercial and not for safety reasons. Any other MAs held by Lupin Group of companies within EU have not been launched yet. Therefore an extension of deadline for submitting the RMP (including the outline of DUS, PASS and educational material) was received by the Reference Member State (RMS) authority BfArM on 29 November 2013 as the products are currently not marketed.

This protocol covers a design for a DUS based on the information captured in longitudinal patient-level databases and has been designed to fulfill the conditions of the authority.

8. Research question and objectives

The Flupirtine DUS aims to characterise prescribing practices of flupirtine-medicinal products during routine clinical use and to assess the main reasons for prescription by representative groups of prescribers.

The analysis will display by specialty and by prevalent/incident status:

- Number of prescribing physicians
- Region of office (East/West Germany)
- Number of overall patients in the office
- Number of patients with at least one flupirtine containing product

- Patient characteristics: age, gender, insurance status, indication for Flupirtine prescription
- Flupirtine exposure:
 - Number of Flupirtine prescriptions per patient during the 12-month observation period
 - Recommended daily Flupirtine dose (by physicians)
 - Recommended Flupirtine treatment duration (by physicians)
 - Prescription length
 - Indications related to the Flupirtine prescription
 - Co diagnosis within analysis period
 - Concomitant prescription of drugs grouped by relevant ATC classes (Annex 3- ii)
- Administered long-term medications (>14 days) leading to contraindication use of Flupirtine
- Contraindications for use of NSAIDs or weak opioids
- Treatment patterns if available
- Liverfunctions test performed within 1 week after Flupirtine exposure start

9. Research methods

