9.2. Setting

The study will be conducted in the outpatient setting in Germany.

Study population

All patients with a record of Flupirtine prescription during the defined 12-month periods (patient selection window) will be identified from selected database.

The study will include both single users and recurrent users of flupirtine-containing medicinal products.

The study will include two cohorts of patients:

- patients initiated on flupirtine treatment after the review of SmPC in Germany
- patients treated with flupirtine before the review of SmPC in Germany

The two cohorts will include:

- Incident user: patients who had one or more flupirtine prescriptions during the one-year observational period, but no flupirtine prescription for at least 12 months prior to the first flupirtine prescription during the observational period
- Prevalent user: patients who had one or more flupirtine prescriptions during the one-year observational period and at least one flupirtine prescription during the 12 months prior to the first flupirtine prescription during the observational period

Inclusion criteria:

Eligible patients must have at least one prescription of Flupirtine (exposure) during the defined 12-month observational period.

Exclusion criteria:

Exclusion criteria will not be applied.

Study period

The selection of patients from the IMS[®] Disease Analyzer will be carried out in two defined 12-month periods from January 1, 2012 to December 31, 2012 and January 1, 2014 to December 31, 2014, respectively (patient selection window). The date of the first prescription fill in each period will be defined as the exposure start date.

Pre-exposure period:

In order to obtain information about medical history before Flupirtine exposure start, a time period of at least 12 months prior to the individual Flupirtine exposure start date will be analysed for each patient for whom these data are available.

Follow-up:

A follow-up period of one to six months after the exposure start date will be monitored for all patients, and till the end of analysis period for whom these data are available.

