9.7.2.2 Flupirtine exposure

Flupirtine exposure will be defined as one or more prescriptions of Flupirtine. These prescriptions will be identified using the ATC code for Flupirtine or INN. The Flupirtine exposure start date (i.e. the cohort entry date) for each patient will be defined as the date of the first record of Flupirtine prescription during each of the defined twelve-month patient selection window.

Treatment duration

The treatment duration (in days) will be evaluated by using the recommended treatment duration by the physician. If this is not available, the treatment duration cannot be determined exactly as the dose recommendation “as required (pro re nata)” is very often given in the therapy of acute pain. Therefore, the percentage of patients with no information according to recommendation by the physician will be determined.

Prescription length

The prescription length (in days) will be determined as follows:

- For prescriptions with available information on recommended dose per day: from the prescription date plus the expected number of days of drug supply based on the package size and the recommended daily dose
- For all prescriptions without recommendation of dosage: from the prescription date plus the expected number of days of drug supply based on the package size and the DDD(400 mg / day)

The prescription length is therefore not necessarily identical to the treatment duration.

The following parameters will be considered in the analysis for each Flupirtine prescription:

- Date of prescription
- Recommended daily dose by physician
- Recommended treatment duration by physician

Analyses:

- Number and percentage of patients with prescriptions of a flupirtine-containing medicinal product during the 12-month patient selection window
- Treatment duration in days
- Prescription length
- Single use and repeated use

Treatment episodes

A treatment episode will be defined as one or more prescriptions (repeated prescriptions) of flupirtine with gaps between prescription length not more than 7 days. In the case the gap between the prescriptions is longer than 7 days it will be considered as two subsequent treatment episodes. The analysis of treatment episodes will consider prescription length based on DDD, because for all prescriptions this information will be available.

Analyses:

- Number and percentage of episodes
- Min, max, mean, median length of episodes
- Patients within each episode

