9.7.2.4 Comparison of the patient/prescriptions of the two observational periods

The comparison of the patients/prescriptions of the two observational periods (assessment period and reference period) based on IMS[®] Disease Analyzer data will consider the following parameters. The comparisons will be performed separately by physician panel and will be stratified by incident and prevalent users:

- Number and percentage of patients with any diagnosis of disease contraindicated for NSAIDs or weak opioids
- Number and percentage of prescriptions with diagnosis associated with acute pain
- Number and percentage of patients with single and repeated flupirtine prescriptions within the defined time period
- Number and percentage of prescriptions with LFT monitoring during flupirtine treatment
- Length of treatment episodes
- Number and percentage of patients with at least one treatment episode longer than 14 days (based on DDD)

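### For prevalent users, counting from the first in-window prescription can record the tail of an ongoing course as single use with a shortened episode, and sometimes as an episode of 14 days or less

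*Protocol*

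**What the plan says.** - **Exposure start.** Section 9.7.2.2 says that the exposure start, which is also the cohort entry date, "will be defined as the date of the first record of Flupirtine prescription during each of the defined twelve-month patient selection window". Section 9.2 gives the same rule. Neither treats prevalent users differently.
- **Prevalent user.** Section 9.2 requires "at least one flupirtine prescription during the 12 months prior to the first flupirtine prescription during the observational period". It does not require that treatment is still running at the window start.
- **Counts.** Section 8 lists "Number of Flupirtine prescriptions per patient during the 12-month observation period". Section 9.7.2.4 compares between periods "Number and percentage of patients with single and repeated flupirtine prescriptions within the defined time period".
- **Episodes.** Section 9.7.2.2 defines an episode as "one or more prescriptions (repeated prescriptions) of flupirtine with gaps between prescription length not more than 7 days", with length based on the DDD of 400 mg/day. Section 9.7.2.4 compares episode length and the share of patients with an episode longer than 14 days.
- **Earlier data.** Section 9.2 gives the purpose of the 12-month pre-exposure period: "In order to obtain information about medical history before Flupirtine exposure start". Joining episodes across the window start is not mentioned.
- **Stratification.** Sections 9.7.1 and 9.7.2.4 report incident and prevalent users separately.

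**The concern.** The two-week limit is a central restriction behind this study. Single versus repeated use, episode length and the share with an episode over 14 days are the compared parameters that bear on it. A prevalent user has, by definition, an earlier prescription that the plan reads in order to classify the patient. If that prescription belongs to the same continuous course, starting the clock at the first in-window prescription hides the earlier part of the course. The tail of long use can then look like short, single use.

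The rule is the same in both years, but its effect depends on how many courses cross each window start and how they end. The July 2013 healthcare professional communication and the September/October 2013 SmPC revisions lie between the two windows, so there is no reason to expect equal numbers. If long-term users were being wound down around the turn of 2014, more of them would have only a last prescription in that window, and 2014 would look better than it was. If most had already stopped during 2013, fewer 2014 courses would be cut, and 2012 would be the year flattered.

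**Working it through.** **1. The plan's own figures.** Table 2 reproduces: 11,284 × 0.75 = 8,463 (PCP) and 1,821 × 0.75 = 1,365.75, stated as 1,365 (orthopaedist). These totals are not split into incident and prevalent users, so they cannot size the problem.

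**2. Single use.** A prevalent user has at least one prescription in the prior 12 months and at least one in the window, so at least two in all. With exactly one in the window, the in-window count gives single. This follows from the stated definitions and needs no assumption about packs.

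**3. Over 14 days.** At 400 mg/day, 14 days of supply is 14 × 400 = 5,600 mg, or 56 units of 100 mg or 14 units of 400 mg. A larger pack exceeds 14 days on its own. The criterion therefore fails wrongly only if all of these hold:
- the episode is not joined to earlier prescriptions;
- its in-window supply is at most 14 DDD;
- the patient has no other in-window episode over 14 days.

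Example with assumed 14-day supplies: prescriptions on 20 December and 3 January have a gap of 0 days. Joined, the episode lasts 14 + 14 = 28 days. In-window only, it lasts 14 days and is not counted as longer than 14.

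**4. Size among carried-over users (illustration).** Take a continuous course of about L days made of k = L/P prescriptions (rounded) of P days each, with start dates uniform in time. If the course has at least one prescription on each side of the window start, that start is equally likely to fall in any of the k − 1 gaps between consecutive prescriptions. So:
- share with one in-window prescription = 1/(k − 1);
- share with in-window length of 14 days or less = floor(14/P)/(k − 1).

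L = 60 is the average treatment duration that section 7 gives for the reported liver cases, used here only as a scenario. L = 180 and all values of P are assumptions.

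| L | P | k | Recorded as single | Recorded as 14 days or less |
|---|---|---|---|---|
| 60 | 7 | 9 | 1/8 = 12.5% | 2/8 = 25% |
| 60 | 10 | 6 | 1/5 = 20% | 1/5 = 20% |
| 60 | 14 | 4 | 1/3 = 33% | 1/3 = 33% |
| 60 | 20 | 3 | 1/2 = 50% | 0% |
| 60 | 30 | 2 | 1/1 = 100% | 0% |
| 180 | 7 | 26 | 1/25 = 4% | 2/25 = 8% |
| 180 | 10 | 18 | 1/17 = 6% | 1/17 = 6% |
| 180 | 14 | 13 | 1/12 = 8% | 1/12 = 8% |
| 180 | 20 | 9 | 1/8 = 12.5% | 0% |
| 180 | 30 | 6 | 1/5 = 20% | 0% |
| 180 | 50 | 4 | 1/3 = 33% | 0% |

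A simulation with 400,000 start dates per scenario agreed to within about half a percentage point. If earlier prescriptions are joined by the 7-day rule and counted, both shares become 0% in every row.

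**5. Effect on the comparison.** Let c be the share of prevalent users with a carried-over course and m the misclassified share from the table. The prevalent-stratum percentage is off by c × m in each year, and the between-year difference by c × m for 2014 minus c × m for 2012. The protocol gives neither c nor the pack sizes that determine m, so neither size nor sign can be fixed.

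**The case against.** The sentence on exposure start sets a cohort entry date and does not define where an episode begins. The 7-day rule carries no window restriction, and treatment of an episode at the window edge is the kind of detail that an analysis plan may settle; section 9.8 says that one will exist. This largely stands: nothing in the protocol says that earlier prescriptions are dropped. In-window episodes remain the natural reading, because section 6 ties data collection to the selection window, section 9.2 describes the look-back as medical history, and section 9.7.2.2 equates exposure start with cohort entry.

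A reader might also infer that every prevalent user with one in-window prescription is mislabelled. The documents do not support that. Prevalent does not mean ongoing: a patient treated 11 months earlier for separate pain is prevalent, and that patient's one in-window prescription is informative. As a literal in-window count, single is also correct. The trouble lies in reading it as a measure of use when the prescription ends a continuing course.

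Stratification fully protects incident users, who have at least 12 flupirtine-free months. It does not resolve the prevalent stratum, which mixes finished and running courses and has its own between-year comparison.

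Finally, a heavy-handed remedy would do harm. Barring prevalent users from the single category fixes that parameter at 0% in both years. Using only full episode lengths would bring 2013 prescribing into the 2014 results.

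**Conclusion.** The point holds in a limited form. It is firm for single versus repeated use: the stated in-window count records the last prescription of a continuing course as single, whatever the pack size. For episodes it is conditional. On the natural reading every carried-over episode is shortened. Misclassification on the 14-day criterion needs, in addition, in-window supply of at most 5,600 mg and no other long episode in the window.

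Under the assumptions above, among carried-over users with 60-day courses, 12.5% to 100% are recorded as single and 0% to 33% as 14 days or less. For 180-day courses the ranges are 4% to 33% and 0% to 8%. These are not shares of all prevalent users, still less of all patients. A reader might infer that the pre-post comparison is biased towards showing compliance. The documents support only that the error need not cancel; its direction depends on when long-term users stopped, which is not given.

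**What to change.** - **Section 9.7.2.2, 14-day criterion:** state that an episode running at the window start is joined to pre-window prescriptions by the same 7-day gap rule when deciding whether it exceeds 14 days.
- **Section 9.7.2.2, episode length:** report it both joined and in-window only, with carried-over episodes flagged and counted for each year.
- **Section 9.7.2.4:** for prevalent users, label the count as one prescription in window, and base the interpretation of single versus repeated use on incident users.

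The cost is a few sentences and some extra programming; earlier prescriptions must already be read to classify users. The prevalent-user results may look less favourable and will include some pre-window prescribing, which is why both versions of episode length should be shown.

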9.7.2.3 Monitoring of liver function

For patients where liver function tests after Flupirtine exposure are available (within 1 week after Flupirtine prescription) the following tests will be analyzed in the PCP and orthopaedist panel. Although a feasibility check has shown that laboratory tests are more comprehensively covered in the PCP panel of the database than in the specialist panels, liver function test will also be monitored in the orthopaedist panel in order to ensure comprehensiveness of data.

However, the laboratory tests of the orthopaedist panel will only be included in the analysis in the case sufficient liver function test data are available. A minimum number of 100 laboratory test results per time period will be considered as sufficient.

As Flupirtine treated patients happen to have false positive Bilirubin results, Bilirubin will not be considered the analysis²¹

The proportion of prescriptions with at least one liver function tests within 1 week after prescription date of flupirtine will be estimated.

Liver function tests

- GOT
- GPT
- Gamma-GT
- AP
- Albumin

Analyses:

- Number and percentage of patients with test available
Value of the test

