The PRAC initiated a subsequent benefit-risk evaluation and considered that the controlled clinical studies required by the Note for guidance on clinical investigation of medicinal products for treatment of nociceptive pain (CPMP/EWP/612/00, issued 21 November 2002) for long-term treatment of chronic pain are not available for flupirtine-containing medicinal products². Based on the fact of observed liver effects recorded during long-treatment with Flupirtine and on the absence of controlled long-term clinical studies, the PRAC noted that the management of chronic pain is no longer favourable in terms of the benefit-risk balance for flupirtine-containing medicinal products. The PRAC adopted a recommendation on 13 June 2013 under the provisions of article 107i of Directive 2001/83/EC³.

Taking the currently available data into account, the PRAC decided that the benefit-risk balance for flupirtine-containing products is favourable in the treatment of acute pain, subject to implementation of the following risk minimisation measures⁴:

- Limitation of indication to acute pain in adults if treatment with other analgesics (e.g. NSAIDs, weak opioids) is contraindicated.
- Restriction of Flupirtine use to a maximum of two weeks of treatment.
- Contraindication of Flupirtine in patients with pre-existing liver disease or alcohol abuse.
- Contraindication of Flupirtine in patients concomitantly taking other medications which are known to cause Drug Induced Liver Injury (DILI).

- Weekly liver function tests during treatment and discontinuation in the case of abnormal liver function tests or clinical symptoms.

The PRAC imposed a DHPC, which was distributed on 15 July 2013, in order to communicate the outcome of the PRAC/EMA decision to healthcare professionals⁵. The SmPCs for flupirtine-containing medicinal products have been revised accordingly by Lupin in February 2014 and MAHS marketing flupirtine-containing medicinal products in September/October 2013⁶. The educational material was distributed in February 2015.

Patients and prescribers have been provided with joint educational material according to the PRAC request, prepared jointly by all German MAHs. The educational material, the DUS and a PASS protocol are parts of the RMP.

As of 5 September 2013, the European Commission implemented the decision (C(2013) 5788 final) with the majority opinion of the CMD(h) addressed to all member states based on the PRAC's recommendation⁷.

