9.5. Study size

All patients in the PCP and orthopaedist panel of the IMS[®]DA fulfilling the selection criteria will be considered for the study.

A preliminary count of patients treated with Flupirtine over a 12-month period (July 2013 to June 2014) gave the sample sizes for the selected IMS[®] DA panels (presented in Table 2). As acute pain treatment has no seasonal impacts, the 12 months period and not a calendar year period is acceptable for feasibility appraisal.

Table 2: Number of patients with flupirtine-containing prescriptions in the IMS[®] Disease Analyzer from July 2013 to June 2014

IMS [®] DA Panel	Number of Flupirtine patients	Number of Flupirtine patients with at least 12 months history	Number of Flupirtine patients with at least 12 months history (25% reduction)
PCP	14,743	11,284	8,463
Orthopaedist	4,635	1,821	1,365

Taking into account the sample sizes and a further 25% reduction for a hypothetical decrease in Flupirtine prescriptions over the planned observation period compared to the period evaluated in 2014, we expect that the minimum number of Flupirtine patients available for the analysis will be not lower than about 8,400 and 1,300 patients in the DA PCP and orthopaedist panel, respectively. The more data are available, the higher the level of confidence on any estimates, i.e. the smaller the width of the 95% confidence interval.

Similar Flupirtine patient counts for the DA database are expected for the 12-month selection window of the Flupirtine DUS.

The study size of the Flupirtine DUS is expected to range from approximately 1,300 Flupirtine patients in the orthopaedist panel of the IMS[®] DA database. The study size is based on the number of patients with Flupirtine prescriptions in the 12-month period from July 2013 to June 2014, so the study size of the planned 12-month patient selection window in the Flupirtine DUS may be slightly different.

The 12-month patient selection window is considered to be sufficient to provide representative for prescribing practices during the routine clinical use of flupirtine-containing medicinal products in Germany.

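### The 100-result minimum makes reporting of the orthopaedist liver-test proportion depend on that proportion's own numerator, so low recorded testing can remove it and its 2012 versus 2014 comparison

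*Protocol*

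**What the plan says.** Protocol section 9.7.2.3 sets a condition for one panel only: "the laboratory tests of the orthopaedist panel will only be included in the analysis in the case sufficient liver function test data are available". It then defines sufficiency: "A minimum number of 100 laboratory test results per time period will be considered as sufficient". The reason given is that "a feasibility check has shown that laboratory tests are more comprehensively covered in the PCP panel of the database than in the specialist panels". The PCP panel has no such condition.

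The same section names the outcome: "The proportion of prescriptions with at least one liver function tests within 1 week after prescription date of flupirtine will be estimated". Its list of analyses gives the number and percentage of patients with a test alongside the test values. Five analytes are listed: GOT, GPT, gamma-GT, AP and albumin.

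Section 9.7.2.4 makes this outcome one of six parameters compared between the reference and assessment periods: "Number and percentage of prescriptions with LFT monitoring during flupirtine treatment". It adds: "The comparisons will be performed separately by physician panel and will be stratified by incident and prevalent users". Section 7 lists the risk minimisation measure behind it: "Weekly liver function tests during treatment and discontinuation in the case of abnormal liver function tests or clinical symptoms".

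No sentence exempts the proportion tested from the minimum. None says what is reported if the minimum is not met.

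**The concern.** The quantity of interest is a proportion: prescriptions (or patients) with a recorded liver test, divided by all flupirtine prescriptions (or patients). The number of test results drives its numerator. A rule that admits the analysis only when this number is large enough makes publication of the estimate depend on the estimate, and low values are the ones at risk of disappearing.

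Liver-test monitoring is one of the measures whose uptake the study describes before and after the SmPC revision. If the orthopaedist figures fall below the minimum, the report would give liver-test monitoring for the PCP panel alone, and the reader could not tell how low the orthopaedist figure was.

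The unit adds a second difficulty. One blood sample can yield up to five listed results, so the same count can come from very different numbers of tested patients.

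**Working it through.** **Inputs.** Section 9.5, Table 2, orthopaedist row: 4,635 flupirtine patients, 1,821 with at least 12 months of history, and 1,365 after a 25% reduction. Section 9.7.2.3: a minimum of 100 results per period and five listed analytes. The protocol gives no prescription count, so patients stand in for prescriptions. Table 2 covers July 2013 to June 2014, not either study year. The number of results per tested patient, r, is not given; I assume r = 1 to 5. Repeat testing could push r above 5 and the cut lower still.

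**The plan's own figures.** 1,821 × 0.75 = 1,365.75 (stated 1,365) and 11,284 × 0.75 = 8,463 (stated 8,463). Both reproduce. The figure of 100 has no derivation in the protocol.

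**What the minimum means as a proportion.** Tested patients needed = 100 / r. This is 100 at r = 1 and 20 at r = 5.

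| Denominator | r = 1 (100 tested) | r = 5 (20 tested) |
|---|---|---|
| 1,365 | 7.33% | 1.47% |
| 1,821 | 5.49% | 1.10% |
| 4,635 | 2.16% | 0.43% |

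**How inclusion follows the testing rate.** With N = 1,365, the chance of meeting the minimum in one period is P(X ≥ 100 / r), where X is binomial(N, p) and p is the true recorded-testing proportion.

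- r = 1: about 0.0001 at p = 5%, 0.33 at 7%, 0.83 at 8% and 0.9997 at 10%.
- r = 5: 0.06 at p = 1%, 0.57 at 1.5% and 0.94 at 2%.

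In both cases inclusion moves from very unlikely to very likely over a narrow range of p.

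**Is the proportion estimable below the minimum?** Exact (Clopper-Pearson) 95% CIs with N = 1,365:

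- 0 tested: 0% (0 to 0.27%)
- 10 tested: 0.73% (0.35 to 1.34%)
- 50 tested: 3.66% (2.73 to 4.80%)
- 99 tested: 7.25% (5.93 to 8.76%)

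With N = 4,635, 99 tested gives 2.14% (1.74 to 2.59%). The counts of 50 and 99 would fall below the minimum only if results per tested patient were few: under 100/50 = 2 and under 100/99 ≈ 1.01 on average. These intervals cover sampling error only. They say nothing about tests that were done but not recorded.

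The incident/prevalent split widens them. If 1,365 were halved to 682 (assumed), zero tested would give an upper limit of 1 − 0.025^(1/682) = 0.54%, which is still informative.

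**The period comparison.** Take assumed rates of about 3% in 2012 and 12% in 2014, with 1,365 patients each: 41/1,365 = 3.00% and 164/1,365 = 12.01%. The difference is 9.01 points. Its SE is √(0.0300 × 0.9700/1,365 + 0.1201 × 0.8799/1,365) = 0.0099, so the 95% CI is 7.1 to 11.0 points. At r = 1, 2012 has 41 results and fails while 2014 has 164 and passes. At any r below 100/41 ≈ 2.4, 2012 still fails. The comparison is then unavailable, whether the rule removes one period or both.

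**The case against.** **The minimum may cover test values only.** Its subject is laboratory tests and test results. The sentence on the proportion comes later and carries no condition, and section 9.7.2.4 lists the comparison by panel with no orthopaedist exception. This reading is open, and a minimum count is reasonable for summarising values. But the condition governs inclusion in the analysis, and that section's analyses include the percentage of patients with a test. If only values were meant, one sentence would settle it.

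**The rule answers poor data capture, not imprecision.** Section 9.7.2.3 says laboratory coverage is weaker in specialist panels. Section 9.9 adds that care outside the practice is not recorded and that patients cannot be followed across panels, so a test done by a PCP for an orthopaedist's patient is invisible. This stands. A reader might infer that the rule conceals non-monitoring by orthopaedists; the documents do not support that, because a low count may reflect incomplete capture. Equally, a count of results cannot tell non-recording from non-testing, so it does not solve the capture problem.

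**The rule does not favour good results as such.** A reader might infer that the panel is reported only when monitoring looks favourable. That does not follow: at five results each, 20 tested patients suffice, which is 1.5% of 1,365 and hardly favourable.

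**One failing period need not remove the other.** A reader might infer that few tests in 2012 would delete the 2014 figure. The protocol does not say so.

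**The weight is limited.** The study is descriptive, with no statistical tests (Annex 2). Liver tests are reported as far as available (section 9.3), and this is one of six comparison parameters. Orthopaedist patients are 4,635/19,378 = 24% of the Table 2 patients, or 1,365/9,828 = 14% of the expected minimum. All of this bears on importance, not on whether the rule is sound.

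**Conclusion.** The point holds. As written, section 9.7.2.3 makes reporting of the orthopaedist liver-test proportion conditional on a count that drives that proportion, and nothing exempts it. Low recorded testing can therefore remove this panel's liver-test analysis and its comparison between 2012 and 2014. The panel's other analyses are unaffected.

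The implied cut is not fixed. It lies at about 1.5% to 7.3% of 1,365 patients, or 0.4% to 2.2% of 4,635, depending on how many results are recorded per tested patient. These figures rest on patients standing in for prescriptions, on 1 to 5 results per tested patient, and on Table 2 counts from July 2013 to June 2014.

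Whether one failing period removes both is left open, but the comparison is lost either way. The finding concerns recorded testing; it does not show that orthopaedists failed to monitor, nor that the rule was meant to hide such a result.

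**What to change.** In section 9.7.2.3, state that the proportion of prescriptions and of patients with at least one recorded liver test will be reported, with its 95% CI, for both panels and both periods whatever the count. Describe it as recorded testing and attach the coverage caveat from sections 9.7.2.3 and 9.9. Confine the minimum of 100 to summaries of test values, and say what is shown for values when a period falls short. Section 9.7.2.4 can then stand unchanged.

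A sensitivity table limited to practices that recorded any laboratory result in the period is optional. It would help with non-recording, but it selects practices by recording behaviour and still misses tests done elsewhere.

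The main change costs a sentence or two and needs no new data. The downside is that a low orthopaedist figure must be published with a caveat that it may reflect incomplete capture.
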